Despite improved access to non-PrEP HIV prevention services in *Anza Mapema*, only interventions including PrEP are likely to bring HIV incidence below the reproductive threshold in this population. After the main study ended, the *Anza Mapema PrEP* cohort enrolled 167 men to receive PrEP services in line with current Kenyan recommendations for key populations, enhanced by the social activities described above. This demonstration program, funded by *Evidence for HIV Prevention in Southern Africa* (EHPSA), aimed to provide evidence on PrEP adherence over 12 months of follow-up, and is cited as part of NASCOP’s *Framework for the Implementation of Pre-Exposure Prophylaxis in Kenya*. HIV-negative MSM  $\geq$ 18 years were enrolled if they reported recent unprotected anal sex,  $\geq$ 3 male sex partners, STI, transactional sex, or injection drug use. All participants were offered PrEP at baseline, with adherence counselling at each visit. Follow-up occurred at week 2; months 1, 2 and 3; then quarterly for 1 year. Adherence was measured by visual analogue scale (VAS) and qualitative self-rating. Dried blood spots were collected at months 3 and 9 for TFV-DP testing. Generalized estimating equations (GEE) with robust variance were used to detect associations with (1) TFV-DP detection and (2) protective TFV-DP levels ( $\geq$ 700 fmol/punch, compatible with  $\geq$ 4 weekly doses).

DBS were provided at 275 visits by 161 participants. At baseline, median age was 26, 46.6% reported unprotected anal sex, 86.5% reported  $\geq$ 3 male partners, 9.8% reported a recent

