A training manual is being designed for the six peer facilitators who will deliver the intervention. This manual will include the didactics and background information necessary to teach the peers the rationale and procedures of the intervention. Training components will be illustrated using role-play exercises, discussion of sample cases, and hypothetical problem scenarios. Peer training will be carried out over 3-4 days at least one week prior to the pilot test, and will include an overview of the study design, theoretical principles, and rationale, as well as step-by-step review of supporting manuals and handouts, practice role-playing exercises, and feedback. Practice sessions will be role-played until each intervention is adequately delivered, as assessed by the research team. We will hold weekly peer facilitator meetings to review study progress, guidelines, and issues that have arisen. Minutes of these meetings will be used to monitor the study and identify needs for revised training or procedures.

Optional intervention components. Once participants have completed the four weekly sessions, peer facilitators will send regular messages to participants to check in with them. If participants choose, they may continue to meet with their peer facilitator for additional iNSC sessions by phone or in-person (this is an optional component of the intervention). Participants may also choose to attend group sessions focused on LGBTI mental health and wellbeing that will be held at NYARWEK (also an optional component of the intervention).

Exit interviews. On completion of each pilot participants' 3 months of follow-up, an in-depth exit interview will be conducted for feedback regarding intervention components and overall study experiences, including any social harms (i.e., inadvertent disclosure, breach of confidentiality) of participation. Participants will be reimbursed KSh 500 for the exit interview. The topic guide for the exit interviews is included in "[Appendix E: Shauriana Exit Interview Guide](#)."

Pilot data analysis. Data from the pilot study will be reviewed on a weekly basis and corrections to ACASI skip rules or other data programming problems will be made immediately. Feedback from participants after intervention sessions and notes taken during interviews will be

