reviewed by the team and discussed at weekly meetings. At the conclusion of the pilot study, we will assess whether we need to revise the intervention based on pilot test findings. If this is the case, we will submit revisions to the ethical review board at Maseno University and to the human subjects research committee at the University of Washington for approval.

**Aim 2 Procedures: RCT of the Shauriana Intervention.** Aim 2 work will use an RCT design to test the acceptability, feasibility, and safety of the **Shauriana** Intervention compared to standard care and estimate initial effect size. Acceptability will be assessed using Likert scales in participant ACASI questionnaires and qualitative exit interviews with participants in each study arm. Feasibility will be assessed at regular research team and peer facilitator meetings, which will be minuted. Safety will be assessed through careful monitoring of study participants to identify and report any adverse events. Information on perceived or experienced social harms and benefits will be collected by study staff at all clinic visits and assessed in greater depth in qualitative exit interviews. Additional trial outcomes that will be monitored and reported include screening and enrollment numbers, visit and intervention attendance, overall retention, and self-reported PrEP uptake and adherence. At the end of the trial, urine samples will be tested for tenofovir (TFV) drug levels (see Laboratory details, below). Dried blood spots will also be collected and stored for future testing of TFV-DP and FTC-TP levels, should funding permit.

Recruitment. The **Shauriana** Intervention pilot RCT will enroll 60 HIV-negative men (30 in the intervention and 30 in SOC) and follow participants for 6 months. We will recruit 60 participants over the course of 3 months; this target is realistic, given enrolment of over 160 men in the **Anza Mapema PrEP** cohort within a 2-month period. Potentially eligible participants will be recruited by NYARWEK, then referred to the **Anza Mapema** Clinic for screening and consenting, as described on pp. 11-12.

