Trial enrollment and randomization. Once consent has been given, participants will be randomized to a study arm. The process of randomization to one of two study arms will be explained carefully and reviewed as part of the informed consent process. Computer-generated randomization will be used to assign participants in a 1:1 ratio to the standard care or intervention group, in blocks of 4, to ensure that equal numbers are randomized across arms. Numbered envelopes indicating the assignment will be prepared in and sealed by the UW CFAR Biometrics Core; study staff will not be aware of an individual's condition until the envelope is opened.

Clinic visits. Consistent with the latest Kenyan guidelines, all trial field-test participants will undergo study procedures at baseline, month 1, month 3, and month 6 at the **Anza Mapema** clinic. As for the pilot study, clinic visits will include HIV counselling and testing, screening for STI symptoms, and individual counselling about HIV prevention methods, including standard of care counselling (information, risk reduction, and PrEP counselling). A standardized physical exam will be performed at each visit, and both blood and urine samples will be collected. For participants taking PrEP, medical history will also focus on PrEP side effects and seroconversion symptoms, and PrEP refills will be provided (monthly for the first 3 months then quarterly). After completing these procedures, RCT participants will complete a detailed ACASI described below. Each of the four clinic visits (baseline, month 1, month 3, and month 6) will take from 1.5 to 2 hours; participants will be reimbursed KSh 500 for each clinic visit.

Standard care. All participants will receive standard care at the *Anza Mapema* Clinic, including standard counseling as described above; screening for depressive symptoms and substance use disorder; monthly *Anza Mapema* peer outreach for education and supply of condoms and lubricants; support group meetings; and social events as described above under “Previous Studies and Rationale.” Attendance at *Anza Mapema* support groups and social events by *Shauriana* study participants will be tracked, as will the content of these group and social events during the study period. To ensure fidelity of delivery for each arm, we will review study progress, procedures, and emergent issues at weekly study meetings.

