Clinical outcomes that will be tracked by the Anza Mapema Clinic using existing data collection instruments include visit attendance, attendance at clinic-sponsored support groups or social events, diagnosis and treatment of STI, HIV test results, PrEP refills, and PrEP-related adverse events and their management. Treatment will be provided for STI syndromes and acute illnesses as needed. All non-scheduled clinic visits will be documented. The study team (both clinic staff and intervention facilitators) will refer participants who need services beyond their capacity to mental health, substance use, advocacy, and/or legal services provided locally. All referrals will be documented.

Men who discontinue PrEP will continue follow-up; PEP will be available for men reporting high-risk exposure while not taking PrEP. Men who seroconvert will be withdrawn from the study and linked to HIV care at *Anza Mapema* or at another HIV clinic of their choice. As described above under “Recruitment,” participants who withdraw before or test positive at the month 1 visit will be replaced; replacement participants in the RCT will undergo randomization and not necessarily be assigned to the arm to which the participant they replace was assigned.

Intervention delivery. Participants assigned to the *Shauriana* intervention will be introduced to an assigned peer facilitator on the day of their enrolment visit, after which telephone, SMS, and/or WhatsApp contacts from peers will begin, with in-person meetings per the intervention schedule described above. For the RCT, the intervention has been expanded to include an initial introductory session where peer facilitators spend time getting to know their assigned participants. Therefore, five core intervention sessions and an optional additional session will be delivered. All peer facilitator contacts with participants and all required and optional intervention sessions will be documented. RCT participants will be reimbursed 350 KSh for their transportation after receiving each of the five core *Shauriana* modules, as participants may need to travel to a safe space for intervention delivery to ensure privacy.

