### **13. Data Management & Statistical Analysis Plans:**

**Data Management Plan:** Recruitment, consenting, and data collection will be monitored carefully to ensure the confidentiality and safety of participants, as detailed in our Human Subjects statement.

**Statistical Analysis Plan:** Data analysis will include both quantitative and qualitative components.

**Qualitative analyses.** Clinic staff and intervention team feedback from meetings will be monitored in real time, to identify any problems needing correction, and then analyzed at the end of the study, to assess feasibility of the intervention, should scale-up for a larger trial seem warranted. Pilot study feedback and pilot/RCT exit interviews will be analyzed to evaluate men’s views regarding the acceptability and overall value of the intervention vs. standard care. In addition, we will review exit interview transcripts to identify best practices for engaging and retaining GBMSM in the **Shauriana** intervention and for optimizing adherence to a daily PrEP regimen and uptake of other HIV prevention services. Notes and tapes from exit interviews will be translated and transcribed into English, then reviewed to identify and code salient themes. NVivo software will be used to facilitate qualitative analysis.

**Primary quantitative analyses.** Acceptability of intervention procedures will be assessed by comparing month 3 and month 6 Likert scale scores for the acceptability of study participation across study arms, using Mann-Whitney U tests. Likert scale scores for **Shauriana** intervention components will be summarized using medians, interquartile ranges, and ranges for intervention participants. Social harms and benefits reported by participants in each arm will be tallied and described in report form.

**Secondary quantitative analyses.** Participant characteristics in the two study arms will be presented using counts and percentages for categorical variables and means and standard deviations or medians and inter-quartile ranges (IQR) for continuous variables. Descriptive statistics will be used to evaluate distributions of the measures assessed at each time-point. To determine validity of the scales used, item scores will be evaluated using Cronbach’s alpha and factor analysis, then compared to published scale psychometrics in African populations if possible. The temporal stability of scales will also be investigated to ensure reliability. These

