approaches will help assess the utility of the instruments used for future analyses and research in HIV-negative Kenyan GBMSM.

Given the preliminary nature of this work and the small sample size dictated by time and budget limitations, secondary analyses will focus on obtaining estimates of Table 2 secondary outcomes (PrEP uptake, adherence, refills, and drug levels) in each group and characteristics associated with these outcomes, for use in design of a larger study. Retention will be compared across study arms using uncorrected Chi square tests in an intent-to-treat analysis. Rates and patterns of self-reported PrEP adherence (defined as taking 4 or more doses per week) will be examined, and assessment methods will be compared using bivariate analyses (e.g., Spearman correlation coefficients for continuous variables). Sociodemographic and other potential cofactors will be evaluated for associations with adherence measures and other outcomes (e.g., urine TFV levels, dried blood spot TFV-DP) using Wilcoxon rank sum or independent-sample t tests, Spearman or Pearson correlations, and chi-square tests as appropriate. Multivariable analyses will adjust for sociodemographic and other potential cofactors. Parsimonious model testing will explore potential intervention efficacy.

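### Intervention men share peer facilitators and control men have none, but the between-arm tests named in Section 13 assume independent men, and the plan does not say how months 3 and 6 are combined

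*Combined protocol and SAP*

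**What the plan says.** All references are to the combined protocol and SAP.

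- **Randomization (Section 11, Aim 2 procedures).** The RCT "will enroll 60 HIV-negative men (30 in the intervention and 30 in SOC) and follow participants for 6 months". Allocation is individual: the scheme will "assign participants in a 1:1 ratio to the standard care or intervention group, in blocks of 4".
- **Facilitators (Section 11).** Men assigned to the "intervention will be introduced to an assigned peer facilitator on the day of their enrolment visit". Facilitators then deliver the one-on-one sessions and later check-ins. The only count is in the Aim 1 text: "A training manual is being designed for the six peer facilitators who will deliver the intervention". The Aim 2 text restates neither the number nor the load per facilitator. It does say: "All peer facilitator contacts with participants and all required and optional intervention sessions will be documented".
- **Primary quantitative analysis (Section 13).** Acceptability is assessed by "comparing month 3 and month 6 Likert scale scores for the acceptability of study participation across study arms, using Mann-Whitney U tests". Scores for the intervention components are only summarized, in the intervention arm.
- **Secondary analyses (Section 13).** Retention is compared between arms by uncorrected chi-square. Cofactors are related to adherence and drug levels "using Wilcoxon rank sum or independent-sample t tests, Spearman or Pearson correlations, and chi-square tests as appropriate". Multivariable and efficacy models are mentioned without a model class or correlation structure. Section 13 does not mention a facilitator effect, an ICC, GEE, a mixed model or a robust variance.
- **Earlier work (Section 8).** In the team's PrEP cohort, "Generalized estimating equations (GEE) with robust variance were used to detect associations". The *Shikamana* trial also used GEE across months 3 and 6.

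**The concern.** Men counselled by the same facilitator may have more similar outcomes than men counselled by different ones. This is plausible here because the relationship with the facilitator is the core of the intervention. The clustering exists in one arm only. A test that treats all 60 men as independent then understates the variance of the intervention-arm result, and one unusually strong or weak facilitator can look like an effect of the intervention.

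There is also a lack of clarity about time. Acceptability, PrEP use, adherence and urine tenofovir are each measured at months 3 and 6. The plan does not say whether the listed tests are run once per visit or on both visits together, and it names no method for correlated visits.

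The trial is declared not powered for effect. However, Aim 2 is to estimate an initial effect size, and Section 13 intends the secondary estimates for designing a larger study. A larger trial delivered by facilitators and sized with no allowance for facilitator variation would be too small if that variation exists.

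**Working it through.** The plan states no power, alpha, effect size or ICC, so there is no figure of its own to reproduce. A two-sided 5% level is assumed.

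**Inputs.** There are 30 men per arm (Section 11, Aim 2) and six facilitators (Section 11, Aim 1). Equal use in the RCT is an assumption and gives m = 30/6 = 5 men per facilitator. The ICC and the within-man correlation rho are assumptions, shown as ranges.

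**Facilitator clustering at one visit.**

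- Design effect in the intervention arm: DE = 1 + (m − 1) × ICC = 1 + 4 × ICC.
- Effective number of intervention men: 30/DE.
- True SE over assumed SE: sqrt(DE) for the intervention arm alone, and sqrt((DE + 1)/2) for the arm difference, because the control arm is not nested.
- Actual error of a nominal 5% test: 2 × (1 − Phi(1.96/R)), where R is the SE ratio for the difference.

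| Assumed ICC | DE | Effective n | SE ratio, intervention arm | SE ratio, arm difference (R) | Actual error, formula | Mann-Whitney, simulated |
|---|---|---|---|---|---|---|
| 0.01 | 1.04 | 28.8 | 1.02 | 1.01 | 5.2% | not run |
| 0.05 | 1.20 | 25.0 | 1.10 | 1.05 | 6.2% | 6.1% |
| 0.10 | 1.40 | 21.4 | 1.18 | 1.10 | 7.4% | 7.1% |
| 0.20 | 1.80 | 16.7 | 1.34 | 1.18 | 9.8% | 9.5% |

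Example at ICC 0.10: DE = 1 + 4 × 0.10 = 1.40; R = sqrt(2.40/2) = 1.095; 1.96/1.095 = 1.79; two-sided error 7.4%.

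The simulated column uses a 5-point scale, six groups of five against 30 independent men, and 6,000 runs per ICC. At ICC 0 it gives 5.0%. Repeat simulations with other settings gave 5.6–5.8%, 6.8–7.4% and 8.5–10.0% at ICC 0.05, 0.10 and 0.20. In simulation, a comparison that respects the facilitator clusters stays at about 5–6%.

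**Two visits.** If each visit is tested separately, each man contributes one value per test and the correlation between visits adds nothing. Retention is also one value per man. If both visits were pooled as independent values, the design effect would be 1 + rho in both arms and the actual error would be 2 × (1 − Phi(1.96/sqrt(1 + rho))):

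- rho 0.3: 8.6%
- rho 0.5: 11.0%
- rho 0.7: 13.3%
- rho 0.8: 14.4%

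Section 13 speaks of tests in the plural but does not say which of the two applies.

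**How well six facilitators can estimate the ICC.** In a one-way analysis of variance with six groups of five, F = (1 + 4 × ICC)/(1 − ICC) on 5 and 24 degrees of freedom. At an estimated ICC of 0.05, F = 1.20/0.95 = 1.263. Dividing by the 97.5% and 2.5% points of F (3.155 and 0.159) gives 0.400 and 7.93. Converting with (F − 1)/(F + 4) gives a 95% interval of about −0.14 to 0.58. At an estimate of 0.10 it is about −0.11 to 0.64.

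**The case against.** The strongest reply is that this is a small pilot that disclaims power, that only acceptability and retention have a named between-arm test, and that at ICC 0.05 the error is about 6% instead of 5%. Six facilitators cannot pin down an ICC, so a clustered analysis recovers little. All of this is true, and it keeps the point modest. It does not remove it: the named tests understate uncertainty for any positive ICC, and an imprecise ICC is better reported with its interval than left out.

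Four stronger readings are tempting, and the documents do not support them.

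- *Every planned analysis assumes independence.* This holds for the named tests only. The multivariable and efficacy models have no stated structure and could allow for correlation.
- *Measuring men twice makes the results too precise.* This happens only if visits are pooled as independent. One test per visit is the more natural reading of Section 13.
- *P-values and intervals for the PrEP outcomes are too optimistic.* Section 13 names no confidence intervals and no between-arm test for these outcomes. It plans estimates in each group, and the listed tests concern cofactors.
- *The value for planning a larger trial is lost.* It is reduced. With individual randomization, ignoring the clustering affects the stated precision and does not in itself bias the arm estimates. Facilitator contacts are documented, so a facilitator term could be added later, although prespecifying it avoids a data-dependent choice.

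**Conclusion.** The concern holds in a limited form. The trial is partially nested, and the named between-arm tests for acceptability and retention ignore this. Over assumed ICCs of 0.01 to 0.20, the SE of the arm difference is 1% to 18% larger than assumed, and a nominal 5% test runs at about 5.2% to 9–10%. The effect is negligible at the low end and worth correcting at the upper end.

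These figures rest on three assumptions: that the six facilitators in the Aim 1 text also serve the RCT, that they are used equally, and the ICC range itself. Fewer facilitators would strengthen the effect.

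On repeated visits, the plan leaves a choice unstated and does not contain a demonstrated error. Only pooling the visits as independent would inflate the error, to about 9–14% for rho 0.3–0.8. This should be changed in the SAP, and it does not threaten the trial.

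**What to change.** 1. State that the listed tests are done separately at month 3 and month 6.
2. For outcomes measured at both visits (acceptability, PrEP use, adherence, urine tenofovir), estimate the arm difference and the cofactor associations with GEE or a mixed model clustered on the man, as the team did in its earlier studies.
3. Keep the ID of each intervention man's assigned facilitator in the analysis dataset. The contact records already planned should supply most of this. State the number of facilitators in the RCT.
4. Prespecify a partially nested analysis, at least as a sensitivity analysis: facilitator as cluster in the intervention arm, each control man as his own cluster, with a small-sample correction.
5. Report outcomes by facilitator and the ICC with its confidence interval. Say that six facilitators give a very imprecise ICC, and plan the larger trial over a range of ICCs rather than on this single estimate.

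The cost is SAP wording, one data field, a little more analysis and slightly wider intervals. The sample size and trial conduct do not change.
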